## ***Secondary analyses***

Secondary analysis will be divided into three main sections:

- a) Effect of functional capacity (WISCI) on aBMD of total hip and femoral neck percent-change; A secondary interaction analysis will be performed for the primary endpoint, exploring the effect of WISCI. The interaction of treatment with WISCI score will be fitted as a fixed effect (in addition to the WISCI score itself), with the resulting estimated treatment differences being shown for continuous scores of the WISCI scale.
- b) Secondary endpoint analysis at 12 months;

The primary analysis described above will be applied for all the three key secondary endpoints at 6, and 12 months visits, with the fixed sequence order described above. Appropriate p-values adjustments to compensate for a possible increased risk in Type I errors due to multiple secondary outcomes measurements will be done using a stepwise Dunnett procedure. All reporting will include both adjusted p values and raw effect sizes.

c) Primary and secondary endpoint analysis at 24 months.

Primary endpoint (total hip and femoral neck aBMD, measured by DXA) and secondary endpoints will be analyzed at 24 months. Here, we will study 4 groups of patients: 24 months of treatment, 24 months of no-treatment, switch from treatment to placebo at 12 months, switch from placebo to treatment at 12 months. A linear mixed model with the four groups, controlling for Baseline aBMD at the hip and ambulatory status measured by WISCI will be fitted to predict percent-change from baseline for each endpoint.

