## Endpoints

**Primary endpoints.** The primary endpoints in this study are the percent-change in aBMD, evaluated by DXA, in the non-dominant (1) total hip and (2) femoral neck skeletal sites. If data on the non-dominant hip are unavailable, we will use aBMD for the dominant hip. Percent-change will be calculated as  $((\text{aBMD}_{\text{follow-up}} - \text{aBMD}_{\text{baseline}}) / \text{aBMD}_{\text{baseline}}) \times 100\%$ .

**Key secondary endpoints.** Secondary endpoints include: (1) integral volumetric bone mineral content (Int.vBMC) distal femoral epiphysis, (2) Int. vBMC tibial epiphysis, and (3) Int.vBMC distal femoral metaphysis measured by QCT. Percent-change will again be calculated for each outcome.

**Additional secondary endpoints.** CT biomarkers: Trabecular volumetric bone mineral density (Tb.vBMD; g/cm^3) and cortical volumetric bone mineral content (Ct.vBMC; g) and bone volume (Ct.vBV; cm^3) at epiphyseal and metaphyseal regions. For the diaphyseal region, Ct.vBMC and Ct.vBV. WISCI.

**Exploratory endpoints.** Torsional strength index (TSI; cm^3) for each skeletal region. Stiffness and strength at the hip, distal femur, and proximal tibia determined by CT-based finite element analysis. Serum markers of bone metabolism: P1NP, BSAP (bone formation markers), and CTX (bone resorption marker).

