## ***Primary analyses***

Group comparisons will be tested with a linear mixed-effects model with the percentage-change from baseline to months 6 and 12 in aBMD at the total hip and femoral neck. Baseline aBMD at the total hip and femoral neck, study visit, ambulatory status measured by WISCI and interaction of WISCI with visit will be fitted as random factors. aBMD by group interaction will be considered statistically significant at  $p < 0.05$ . Raw effect sizes will be calculated as differences between groups at each time point. Multiplicity will be handled by utilizing a fixed-sequence approach to testing, with initial analysis of total hip ( $\alpha=0.05$ ) and if successful followed by femoral neck ( $\alpha=0.05$ ).

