## Analysis Plan Summary

Endpoint	Statistical Method	Model/Covariates	Missing Data	Objective
% Change from Baseline at 6,12 months with total hip and femoral neck aBMD, DXA	MEM	Baseline total hip/ femoral neck aBMD, visit, WISCI score; (subjects as random effects)	MLE	Primary Analysis
% Change from Baseline at 6,12 months with total hip aBMD, DXA	MEM	Baseline total hip aBMD, visit, WISCI score; (subjects as random effects)	Multiple Imputation	Sensitivity Analysis
% Change from Baseline at 6,12 months with total hip aBMD, DXA (a)	MEM	Baseline total hip aBMD, visit, WISCI score, (subjects as random effects)	MLE	Secondary, Interaction Analysis
% Change from Baseline at 6, 12 months with femoral neck aBMD, DXA (b)	MEM	Baseline total hip aBMD, visit, WISCI score; (subjects as random effects)	MLE	Secondary Analysis
% Change from Baseline at 6,12, months with QCT Int.vBMC Femoral Epiphysis (b)	MEM	Baseline total hip aBMD, visit, WISCI score; (subjects as random effects)	MLE	Secondary Analysis
% Change from Baseline at 6,12, QCT Int.vBMC Femoral Metaphysis (b)	MEM	Baseline total hip aBMD, visit, WISCI score; (subjects as random effects)	MLE	Secondary Analysis
% Change from Baseline at 24 months with total hip aBMD, DXA (c)	MEM	Baseline total hip aBMD, visit, WISCI score; (subjects as random effects)	MLE	Secondary Analysis
% Change from Baseline at 24 months with	MEM	Baseline total hip aBMD, visit, WISCI	MLE	Secondary Analysis

femoral neck aBMD, DXA (c)		score; (subjects as random effects)		
% Change from Baseline at 24 months with QCT Int.vBMC Femoral Epiphysis (c)	MEM	Baseline total hip aBMD, visit, WISCI score; (subjects as random effects)	MLE	Secondary Analysis
% Change from Baseline at 24 months with QCT Int.vBMC Femoral Methaphysis (c)	MEM	Baseline total hip BMD, visit, WISCI score; (subjects as random effects)	MLE	Secondary Analysis

(a) Secondary analysis phase 1: Interaction Analysis for primary endpoint with WISCI; (b) Secondary analysis phase 2: Secondary endpoints at 12 months; (c) Secondary analysis phase 3: Primary and Secondary endpoints at 24 months. aBMD (areal bone mineral density); MEM (mixed effects model); MLE (maximum likelihood estimates); WISCI (walking index for spinal cord injury).

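### SAP Secondary analyses (b) sends the three key secondary QCT endpoints to a fixed sequence that does not name them, then adds a stepwise Dunnett adjustment that does not fit several outcomes in two arms

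*SAP*

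**What the plan says.** SAP Primary analyses controls multiplicity by "utilizing a fixed-sequence approach to testing, with initial analysis of total hip" at 0.05 and then, if that succeeds, femoral neck at 0.05. No further step is named.

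SAP Endpoints numbers the key secondary endpoints: "Secondary endpoints include: (1) integral volumetric bone mineral content (Int.vBMC) distal femoral epiphysis", then "2) Int. vBMC tibial epiphysis, and (3) Int.vBMC distal femoral metaphysis measured by QCT". It does not call this numbering a testing order.

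SAP Secondary analyses (b) applies the primary model to these three endpoints at months 6 and 12 "with the fixed sequence order described above". The next sentence says p-value adjustment for "multiple secondary outcomes measurements will be done using a stepwise Dunnett procedure". The paragraph ends: "All reporting will include both adjusted p values and raw effect sizes".

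In the Analysis Plan Summary, three 12-month rows carry the (b) tag. One is a primary endpoint, "Change from Baseline at 6, 12 months with femoral neck aBMD, DXA (b". The second is "Change from Baseline at 6,12, months with QCT Int.vBMC Femoral Epiphysis (b", and the third is the femoral metaphysis. The tibial epiphysis has no row at 12 or at 24 months.

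Four groups appear only in Secondary analyses (c), at 24 months, and (c) gives no multiplicity rule.

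**The concern.** There are two defects. First, the cross-reference leads to a sequence that contains none of the three endpoints. The Endpoints numbering may be what was meant, but the SAP does not say so, and the summary table does not supply the order either.

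Second, a Dunnett procedure handles several treatment groups against a shared control on a single outcome. Up to month 12 the trial has one active arm and one placebo arm, so each outcome has one comparison and Dunnett has nothing to adjust. A Dunnett-type step-down across outcomes can be built from their joint distribution, but the SAP gives no correlation, no way to estimate one, and no choice between step-down and step-up.

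At stake are the claims for the knee QCT endpoints. The promised adjusted p-values cannot be reproduced from the text, and which endpoints count as significant could be settled after the results are known.

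**Working it through.** **Inputs.** Two arms to month 12 (SAP Overview); three endpoints (SAP Endpoints); 0.05 per step (SAP Primary analyses; two-sided assumed, since the SAP does not say); 30 per arm, giving 58 df (Protocol 14.3). Protocol 14.3 expects under 20% drop-out, and 30 × 0.8 = 24 per arm. The documents give no correlation between endpoints, so a range is assumed.

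**Plan's own figures.** Power for d=0.74 with 30 per arm is 80.5% by the noncentral t, against the stated 80%. A declared fixed sequence at 0.05 per step has familywise error equal to the chance that its first test rejects, 5.0%.

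**Familywise error over the three endpoints, no true effect.**
- Dunnett read literally: one comparison per outcome, critical value 1.96, each test at 0.05. If used alone with independent outcomes, 1 − 0.95³ = 14.3%. At correlations 0.3, 0.5, 0.7 and 0.9: 13.6%, 12.6%, 11.0% and 8.3%.
- Dunnett borrowed as a three-comparison step-down (built-in correlation 0.5, 58 df): critical t 2.412, 2.267, 2.002, i.e. p below 0.019, 0.027, 0.05 from the smallest p upward. At true correlations 0, 0.5, 0.8 and 0.9: 5.6%, 5.1%, 4.0% and 3.4%.
- Step-up version: p below 0.05, 0.026, 0.019 from the largest p downward.

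**Do the rules agree?** Constructed raw p-values in the Endpoints order (femoral epiphysis, tibial epiphysis, femoral metaphysis):

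| Rule | 0.06 / 0.001 / 0.001 | 0.030 / 0.035 / 0.040 |
|---|---|---|
| Fixed sequence | 0 of 3 (stops at 0.06) | 3 of 3 |
| Step-down Dunnett | 2 of 3 | 0 of 3 (0.030 > 0.019) |
| Step-up Dunnett | 2 of 3 | 3 of 3 (0.040 < 0.05) |
| Literal Dunnett | 2 of 3 | 3 of 3 |

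In the first case the adjusted p-values are 0.06/0.06/0.06 by fixed sequence (running maximum) and 0.06/0.0028/0.0028 by step-down Dunnett. Neither of these two rules is uniformly the stricter, and the second case shows that the direction of the steps matters too.

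**How often would it matter?** Simulated two-arm trials with equal effects on all three endpoints; percentage in which fixed sequence and step-down Dunnett differ on at least one endpoint, at correlation 0.5 and then 0.8:

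| d | 30 per arm | 24 per arm |
|---|---|---|
| 0.74 | 23.7 / 15.3 | 29.4 / 18.7 |
| 1.0 | 5.6 / 4.1 | 12.0 / 8.2 |
| 1.23 | about 0.6 | about 3 / 2 |

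Here d=0.74 is the protocol's generic detectable effect and d=1.0 its lower figure for the knee by DXA. The third comes from the left distal femur row of Protocol Table 2: difference −3.84 − (−26.68) = 22.84; SD √[(21.99² + 14.29²)/2] = 18.54; d = 22.84/18.54 = 1.23. None is QCT-specific. Protocol 14.3 expects CT variance to be much smaller, so the true rate may lie at or below the bottom of this range.

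**The case against.** The best defence is gatekeeping: test total hip, then femoral neck, then apply a stepwise adjustment within the secondary family. That is a coherent design and would make the two sentences complementary. It is not written, and it would still rest on a procedure that does not fit three outcomes in two arms.

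The Dunnett sentence may also have another target. It does not repeat the word key, so it could cover the additional secondary endpoints, although SAP Exploratory Analyses places additional CT biomarkers there. Or it could belong in (c), where four groups including placebo/placebo make Dunnett a natural choice. Both readings are plausible and the SAP settles neither. A reader might therefore infer that the two rules certainly govern the same three endpoints, or that the sentence should simply be struck out; the text supports neither with certainty.

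It can also be said that the disagreement rates lean on small effects. That stands: at the protocol's own pilot knee effect, disagreement at 30 per arm is about 0.6%. The example p-values are constructed; they show that conflict is possible, not that it is likely.

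**Conclusion.** Wrong as written, and worth correcting. Section (b) states a multiplicity rule that does not do its stated job and cites an order that does not contain the endpoints concerned.

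A reader might infer that the plan inflates type I error. The documents do not establish that. Error of about 8% to 14% follows only if Dunnett is read literally and used alone. A declared fixed sequence holds 5.0%, and the borrowed three-comparison version gives about 3.4% to 5.6%. What is established is that the rule is left open, and that the readings differ both in error control and in the claims they allow.

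A reader might also infer that the primary result is exposed. It is not: the total hip to femoral neck sequence is clear, and only secondary claims are affected. The figures assume two-sided tests, equal effects across endpoints, and endpoint correlations that the documents do not supply.

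**What to change.** In Secondary analyses (b), replace the Dunnett procedure with one rule valid for several outcomes in two arms. The simplest is to continue the fixed sequence after femoral neck in the Endpoints order (distal femoral epiphysis, tibial epiphysis, distal femoral metaphysis), each at 0.05, with adjusted p-values as the running maximum. Holm over the three, once femoral neck succeeds, is an acceptable alternative. State which one produces the reported adjusted p-values.

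State that month 12 is the inferential contrast and month 6 supportive, in line with the heading of (b), the table footnote and Hypothesis 1a. Otherwise each step holds two tests.

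If Dunnett was meant for comparing the other groups with placebo/placebo at month 24, move the sentence to (c) and say so. It would not cover zol/zol against zol/placebo (Hypothesis 1c), which does not involve that control. If it was not meant for (c), delete it.

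In the Analysis Plan Summary, add the tibial epiphysis at 12 and 24 months and remove the (b) tag from femoral neck.

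The cost is SAP wording only, with no extra patients or data. The trade-off is power. A fixed sequence stops at its first non-significant endpoint, while Holm gives up some power on the first. Once the gate is passed, at 30 per arm and correlation 0.5, power for the first, second and third endpoint is 80/69/62% by fixed sequence against 74% each by Holm at d=0.74, and 97/94/92% against 96% each at d=1.0.

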AIM 1: To define the timing and frequency of administration of zoledronic acid 5mg infusion that will result in the optimal prevention of bone loss after acute SCI.

Hypothesis 1: In participants treated shortly after acute SCI with a single infusion of zoledronic acid, the mean loss of bone after both one year (Hypothesis 1a) and two years (Hypothesis 1b) at skeletal sites in the lower extremity (total hip, femoral neck, proximal tibia, distal femur) will be less than that determined for participants who received placebo. The primary hypothesis will focus on changes at the total hip site and the study powered accordingly.

The following additional hypotheses will also be addressed:

Hypothesis 1c: The effects of a single infusion of zoledronic acid after acute SCI will wane over time; retreatment with zoledronic acid after one year will result in greater maintenance of bone than a single infusion with zoledronic acid.

Hypothesis 1d: Initiation of treatment with zoledronic acid at one year after acute SCI in people not previously treated to prevent bone loss will still result in preventing further bone loss compared to no active bone-specific treatment; loss of bone mass that has occurred during the initial year without treatment will not be reversed, however.

To accomplish these objectives, we will undertake a 2 year, double-blinded, randomized, controlled trial. During the first year, participants will be randomized to either zoledronic acid 5 mg or placebo, and evaluated at 3, 6 and 12 months after infusion by DXA and CT imaging to determine changes in bone mass. At the 12 month time point, the participants in each of the treatment groups (zoledronic acid, placebo) will be re-randomized in a 1:1 ratio to receive either an infusion of zoledronic acid 5 mg or an infusion of placebo and followed during a second year of study. During year 2, participants will be evaluated at 6 and 12 months after re-infusion by DXA and CT imaging to determine changes in bone mass. (Subjects weighing less than 40 kg and assigned to receive study drug will be administered a reduced dose of 2 mg instead of 5 mg.)

AIM 2: To evaluate the use of serum markers of bone metabolism to guide therapeutic decisions of timing and need for retreatment with zoledronic acid after acute SCI.

Hypothesis 2: Serum levels of markers of bone resorption will be elevated after acute SCI and suppressed by zoledronic acid infusion. Recovery of bone markers to high levels will correlate

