14.3. Sample size determination

Determination of the sample size for this study is based on 2 factors: the data we have accumulated of BMD changes at various skeletal sites from several of our preliminary studies and from the practical issues related to the number of participants who can be recruited. Both of these approaches provide congruent results. Our preliminary DXA data from participants followed for one year after infusion of zoledronic acid and a comparable group of acute SCI participants in a parallel study who were only observed and not treated for 12 months are presented in Table 2. If one focuses simply on the total hip skeletal site, which is the primary outcome measure, the data suggest a standardized effect size of Cohen’s d of ≥ 3.9 (based on either right or left hip). This effect size would yield virtually 100% power with our planned sample size of $N = 60$. We will also, however, have enough power to detect effect sizes as small as $d = .74$ with 80% power with 30 participants within each group. Another way to express these data is to consider that the largest standard deviation in the BMD measurement at any of the hip sites was 9.02%. If we assume that this will be the standard deviation for all skeletal sites, with 30 participants/group, we will have 80% power to detect a difference of 6.5% between groups.

Region	Zoledronic Acid	Placebo
Spine	3.31 ± 2.11%	-8.04 ± 4.41%
Left Total Hip	-3.40 ± 3.51%	-13.83 ± 2.01%
Left Femoral Neck	4.60 ± 9.02%	-17.60 ± 3.42%
Right Total Hip	-2.80 ± 5.08%	-18.21 ± 2.39%
Right Femoral Neck	-1.10 ± 7.56%	-17.20 ± 4.58%
Left Distal Femur	-3.84 ± 21.99%	-26.68 ± 14.29%

Table 2: BMD changes 12 mo after SCI at various skeletal site

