## Overview

This is a 2-year, randomized, double-blind placebo-controlled study of zoledronic acid to evaluate its efficacy and safety for the prevention of bone loss and maintenance of bone strength in individuals with recent onset SCI (see protocol). Subjects were randomized at the baseline visit to receive either zoledronic acid or placebo. At the end of the first year of the study, each treatment group was re-randomized to either zoledronic acid or placebo to evaluate the durability of response to zoledronic acid and the utility of serum bone markers to guide therapeutic decision making. DXA imaging, CT imaging of knee and bone markers were obtained at baseline, 3 months, 6 months, 12 months, 18 months and 24 months. CT imaging of the hip was obtained at baseline, 6 months, 12 months, and 24 months.

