## Study Objectives/Statistical Hypotheses

**Hypothesis 1a.** In participants treated shortly after acute SCI with a single infusion of zoledronic acid, the mean loss of bone after one year at skeletal sites in the lower extremity will be less than that determined for participants who received placebo. Hip areal bone mass density (aBMD) will be assessed as the primary endpoint.

**Hypothesis 1b:** In participants treated shortly after acute SCI with a single infusion of zoledronic acid (zol/placebo) as well as those receiving a second treatment with zoledronic acid (zol/zol), the mean loss of bone after two years at skeletal sites in the lower extremity will be less than that determined for participants who received placebo for two years (placebo/placebo).

**Hypothesis 1c:** The effects of a single infusion of zoledronic acid after acute SCI will wane over time; retreatment with zoledronic acid after one year will result in greater maintenance of bone than a single infusion with zoledronic acid.

**Hypothesis 1d:** Initiation of treatment with zoledronic acid at one year after acute SCI in people not previously treated (placebo/zol) will still result in preventing further bone loss compared to no active bone-specific treatment (placebo/placebo); loss of bone mass that has occurred during the initial year without treatment will not be reversed, however.

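### Low-cost gain for two secondary hypotheses: the 24-month model for H1c and H1d is not adjusted for the month-12 value, which loses precision

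*SAP*

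**What the plan says.** Protocol Section 2 (Aim 1) describes a second randomisation. At month 12 the participants of each first-year arm "will be re-randomized in a 1:1 ratio to receive either an infusion of zoledronic acid 5 mg or an infusion of placebo". Two SAP hypotheses rest on it. H1c holds that "retreatment with zoledronic acid after one year will result in greater maintenance of bone than a single infusion with zoledronic acid" (zol/zol against zol/placebo). H1d compares placebo/zol with placebo/placebo.

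The month-12 measurement is scheduled for everyone. The SAP Overview says "DXA imaging, CT imaging of knee and bone markers were obtained at baseline, 3 months, 6 months, 12 months, 18 months and 24 months", and hip CT is also due at month 12.

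SAP Secondary analyses, part (c), gives the only 24-month model: "A linear mixed model with the four groups, controlling for Baseline aBMD at the hip and ambulatory status measured by WISCI will be fitted", with percent change from the original baseline as the outcome. The 24-month rows of the Analysis Plan Summary list "Baseline total hip aBMD, visit, WISCI score" with subjects as random effects and maximum likelihood for missing data. Neither place has a month-12 covariate, and neither says which visits enter.

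The only year-2 power in Protocol Section 14.3 is for zol/zol against placebo/placebo. None is given for H1c or H1d.

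**The concern.** For H1c and H1d the relevant randomisation happens at month 12. The endpoint's month-12 value, if measured before the second infusion, is a pre-randomisation covariate for these contrasts. Month-12 and month-24 percent change are both cumulative changes from the same month-0 scan, so some positive correlation is plausible. Leaving out a correlated baseline keeps its variance in the error term.

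At stake is the precision of the answers on retreatment and delayed start, which have at most 15 participants per group.

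**Working it through.** **Inputs.** From Protocol Section 14.3: 15 per group at year 2; drop-out below 20% (12 per group at 20%); and SD 9.02%, since "the largest standard deviation in the BMD measurement at any of the hip sites was 9.02" percent. In Table 2 ("BMD changes 12 mo after SCI at various skeletal site") that SD belongs to the left femoral neck under zoledronic acid. Placebo SDs there include 2.39% (right total hip) and 4.58% (right femoral neck). Alpha is 0.05, taken as two-sided. Assumed, because the documents do not give it: rho, the partial correlation of month-12 with month-24 percent change given baseline aBMD and WISCI. Table 2 SDs are used as residual SDs.

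**Step 1. Reproduce the plan.** SE = 9.02 × √(2/15) = 3.29. The smallest one-year hip difference is 13.83 − 3.40 = 10.43 points. Normal power is Φ(10.43/3.29 − 1.96) = 88.6% (plan: 88%). For 9 points it is 78.0% (plan: 80%). So the plan's year-2 figures assume no month-12 adjustment.

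**Step 2. Detectable difference.** The contrast variance is SD² × (1 − rho²) × (2/n) × [1 + k/(df − k − 1)]. Here k is the number of covariates and df = 4n − 4. The last factor is the cost of estimating the slopes. Power is from the non-central t.

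- SAP model, n = 15, k = 2: factor 1 + 2/53 = 1.038; detectable difference 1.061 SD.
- Plus month 12, k = 3: factor 1 + 3/52 = 1.058; detectable difference 1.072 SD × √(1 − rho²).
- n = 12: 1.199 SD and 1.215 SD × √(1 − rho²).

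| SD, n per group | SAP model | rho 0 | 0.3 | 0.5 | 0.7 | 0.9 |
|---|---|---|---|---|---|---|
| 9.02%, 15 | 9.6 | 9.7 | 9.2 | 8.4 | 6.9 | 4.2 |
| 9.02%, 12 | 10.8 | 11.0 | 10.5 | 9.5 | 7.8 | 4.8 |

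For H1d with 15 per group, placebo-arm SDs apply:
- SD 2.39%: 1.061 × 2.39 = 2.5 points without month 12; 1.072 × 0.866 × 2.39 = 2.2 at rho 0.5.
- SD 4.58%: 4.9 and 4.3 points.

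Break-even at 15 per group is rho = √(1 − (1.061/1.072)²), about 0.14. At rho 0 the cost is 1.072/1.061, about 1%.

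**Step 3. Simulated power.** With four groups of 15, SD 9.02% and a true difference of 6 points, power is about 42% under the SAP model. With month 12 it is 45, 53 and 68% at rho 0.3, 0.5 and 0.7. Type I error is 4.6 to 5.2% for both models.

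**Step 4. If month 12 enters as an outcome visit.** With complete data and a free mean for every group at every visit, the SE of the month-24 contrast stays at 3.29, so nothing is gained. Giving the two re-randomised groups one common month-12 mean reduces it to 2.85, 2.35 and 1.44 at rho 0.5, 0.7 and 0.9, as the covariate does.

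**Step 5. Drop-out.** Assume 20% drop-out in one year-2 arm only, driven by month-12 loss (logistic slope 1.5 per SD, assumed), with true difference 0 and SD 9.02%.
- Month 24 as sole outcome visit: off by about 1.0 point (rho 0.5) or 1.5 points (rho 0.7).
- Same mechanism in both arms: 0.02 to 0.04.
- Months 12 and 24 as outcomes under maximum likelihood with free means: within 0.1 of zero.
- Month 12 as covariate: within 0.05 of zero.

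**Step 6. Why H1b must stay separate.** H1b uses the first randomisation, so month 12 lies after treatment. In a simulation at rho 0.8, one common model with the month-12 covariate reduced the zol/placebo against placebo/placebo difference from 13.1 to 4.2 points.

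**The case against.** The planned analysis is valid. With complete data, leaving out a baseline covariate causes no bias, and no statement in the documents is contradicted. That stands, so this is a suggested improvement.

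The summary table's visit term, random subjects and maximum likelihood suggest that several visits enter, so month 12 may already be used. The SAP does not say so. Under that reading the drop-out bias goes (Step 5), but with free means the precision is not recovered (Step 4).

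The correlation is assumed. That also stands: at rho 0.3 the gain is only 9.6 to 9.2 points, about 4%. All gains further assume that every month-12 scan is usable, whereas Protocol Section 7 (2nd Infusion) allows imaging after the infusion. The share affected is unknown.

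Three stronger readings are tempting, and the documents do not support them:
- *The 24-month contrasts are biased.* This needs both month 24 as the sole outcome visit and drop-out that depends on month-12 loss differently by year-2 arm. The documents establish neither.
- *The 9.02% figures describe H1d.* That SD is from the zoledronic acid arm. H1d compares two placebo-first groups with smaller Table 2 hip SDs, so its absolute differences are smaller.
- *Unequal SDs between first-year arms support this point.* A single pooled residual variance distorts type I error with or without month 12, so that is a separate matter.

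**Conclusion.** The point holds as a low-cost precision gain for H1c and H1d only. The proportional gain in detectable difference is about 4% at rho 0.3, 13% at 0.5 and 28% at 0.7 (9.6 to 9.2, 8.4 and 6.9 points at SD 9.02%), against a loss of about 1% at rho 0. It rests on the assumed rho, on one-year SDs from small preliminary studies, on equal variances and a common slope, and on month-12 scans that precede any effect of the second infusion. The documents give no QCT SD, so the QCT endpoints are not quantified.

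**What to change.** Add to SAP Secondary analyses, part (c):

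- For H1c and H1d only, among re-randomised participants and by assigned group, fit the 24-month model with the same endpoint's month-12 percent change as an added covariate. Alternatively, model months 12 and 24 jointly with one common month-12 mean per first-year arm. Take only the two within-arm contrasts from it.
- Keep the H1b model without month 12.
- State which visits enter each 24-month model.
- Use a month-12 scan as covariate only if it was taken before the second infusion or within a stated short window of it. Treat other scans as a missing covariate and give the rule for that. For illustration, if a late scan already showed 10% of a 5-point effect, adjustment at rho 0.7 would estimate 5 × (1 − 0.7 × 0.1) = 4.65.
- Say how participants who decline re-randomisation (Protocol Section 12) are handled. Those treated at month 6 are already not re-randomised and are censored (Protocol Section 10).

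If year-2 results are already unblinded, label this a supplementary analysis.

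Cost: no new data, but a second model beside H1b and rules for the scan window and the missing covariate. The detectable difference is about 1% larger if rho is near 0 (break-even near 0.14), and the gain shrinks if many month-12 scans fall outside the window.

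### The QCT knee key secondary endpoints are adjusted for baseline hip DXA density rather than their own QCT baseline, which costs some precision, mainly at month 24

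*SAP*

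**What the plan says.** The SAP's Endpoints section defines three key secondary endpoints, all integral bone mineral content by QCT: distal femoral epiphysis, tibial epiphysis and distal femoral metaphysis. Each is analysed as percent change from its own baseline.

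- **Month 24** (SAP, Secondary analyses, item c): a four-group linear mixed model "controlling for Baseline aBMD at the hip and ambulatory status measured by WISCI will be fitted to predict percent-change from baseline for each endpoint".
- **Months 6 and 12** (item b): "The primary analysis described above will be applied for all the three key secondary endpoints at 6, and 12 months visits". The covariates of that primary model are "Baseline aBMD at the total hip and femoral neck, study visit, ambulatory status measured by WISCI and interaction of WISCI with visit" (SAP, Primary analyses), which the text says are fitted as random factors.
- **Analysis Plan Summary:** the QCT rows for femoral epiphysis and metaphysis, at 6/12 and at 24 months, carry the covariate cell "Baseline total hip aBMD, visit, WISCI score; (subjects as random effects"; the 24-month metaphysis row prints BMD for aBMD. The primary row instead has "Baseline total hip/ femoral neck aBMD, visit, WISCI score; (subjects as random effects", so there the baselines of the analysed sites are named. The tibial epiphysis has no row.

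No section names a QCT baseline as a covariate. The protocol (section 7) schedules knee CT before the first infusion.

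**The concern.** The usual covariate for a change outcome is the baseline of the same measurement. Percent change already divides by that baseline, but dividing does not adjust for it: any remaining correlation between baseline and percent change stays in the residual variance, and a chance difference between arms in that baseline carries through to the estimated treatment difference. Here the model uses areal density of the hip by DXA, a different bone and a different modality. It spends the same degree of freedom and recovers only what hip density shares with knee bone content. At stake is the precision of the knee results, chiefly the month-24 comparisons among four groups of about 15.

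**Working it through.** **1. The plan's own knee power.** Inputs are from protocol section 14.3 and its Table 2 (left distal femur, DXA): changes of -3.84% and -26.68%, with SDs of 21.99% and 14.29%. Taking the larger SD, d = (26.68 - 3.84)/21.99 = 22.84/21.99 = 1.039. Power = Φ(d/√(2/n) - 1.96), two-sided 0.05 assumed:

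- n = 30 per group: 1.039/0.258 = 4.02; Φ(2.06) = 98.0% (stated 98%).
- n = 15 per group: 1.039/0.365 = 2.84; Φ(0.88) = 81.2% (stated 81%).

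Both reproduce. They are unadjusted figures, so the choice of covariate does not make them wrong.

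**2. Own baseline against hip.** Let r be the correlation of the QCT baseline with its percent change, and ρ the correlation of hip and knee baselines. Assume hip density relates to knee change only through ρ, so its correlation with change is rρ. Residual variance is then a share 1 - r²ρ² with the hip covariate and 1 - r² with the own baseline. The sample size with hip adjustment that matches 60 participants with own-baseline adjustment is 60(1 - r²ρ²)/(1 - r²). Neither r nor ρ is in the documents.

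| r | Gain on 60, ρ = 0.5 | Gain on 60, ρ = 0.8 |
|---|---|---|
| 0 | 0 | 0 |
| 0.2 | 60 × 0.990/0.96 - 60 = 1.9 | 60 × 0.9744/0.96 - 60 = 0.9 |
| 0.3 | 60 × 0.9775/0.91 - 60 = 4.5 | 60 × 0.9424/0.91 - 60 = 2.1 |
| 0.4 | 60 × 0.960/0.84 - 60 = 8.6 | 60 × 0.8976/0.84 - 60 = 4.1 |
| 0.5 | 60 × 0.9375/0.75 - 60 = 15.0 | 60 × 0.840/0.75 - 60 = 7.2 |

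For a 15 v 15 contrast (30 participants) the gains are half of these.

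**3. Power.** The documents give no QCT SD, so the knee DXA SD of 21.99% stands in.

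- *30 per group:* power moves from 98.0% with no adjustment to 99.6% with own baseline even at r = 0.5. Little is at stake.
- *15 per group:* a simulated two-group ANCOVA (3,000 runs per setting, t-based) gave the following.

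| r | ρ | Hip covariate | Own baseline |
|---|---|---|---|
| 0 | 0.3 | 77.9% | 78.2% |
| 0.3 | 0.3 | 77.7% | 80.4% |
| 0.5 | 0.3 | 78.7% | 87.6% |
| 0.5 | 0.8 | 84.0% | 87.9% |

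The Monte Carlo standard error is about √(0.8 × 0.2/3000) = 0.7 points. Under no effect, the rejection rate was about 4 to 6% with either covariate.

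**4. Chance imbalance at 15 per group.** The baseline difference between two arms has SD √(2/15) = 0.365 baseline SDs. Unadjusted, it shifts the estimate by r times that: at r = 0.3, 0.3 × 0.365 = 0.11 outcome SDs. With hip adjustment the remaining shift is multiplied by √(1 - ρ²): 0.11 × 0.87 = 0.095 at ρ = 0.5 and 0.11 × 0.6 = 0.066 at ρ = 0.8. Own-baseline adjustment removes it.

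**The case against.** **This is efficiency, not validity.** The arms are randomised and the covariate is pre-specified. A reader might infer that the knee comparison is biased, that its type I error is inflated, or that the protocol's 98% and 81% are wrong. None of that follows, as steps 1 and 3 show.

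**The gain may be small.** Percent change already divides by the own baseline, so r near 0 is plausible. CT scans are phantom-calibrated (protocol section 3.6), and section 14.3 expects CT variance to be much smaller than DXA variance, so a large effect of measurement error cannot be presumed. This stands. It is also tempting to quote 60/(1 - r²) - 60, which is 2.5 to 20 participants for r = 0.2 to 0.5. That compares own-baseline adjustment with no adjustment, whereas the SAP does adjust for hip density. For the same reason a knee imbalance is not wholly uncorrected: the hip covariate removes the shared part, and ordinary standard errors allow for chance imbalance on average.

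**It may be a copied table cell.** The separate femoral neck rows also list total hip baseline, although the primary row names the femoral neck. Item (b), read alone, could mean the same model with each endpoint's own baseline. That origin is likely enough, but item (c) states hip aBMD for each endpoint in prose and the table says the same for months 6 and 12. An analyst who follows the SAP will fit the hip covariate.

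**Scope.** A reader might extend the point to all CT, strength-index and finite element outcomes. The Exploratory Analyses section specifies only an approach similar to the primary one for the serum markers and additional CT biomarkers, and gives no covariates for the strength and finite element measures. Hip adjustment there is an inference.

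**Conclusion.** The point holds as a loss of precision and of protection against chance imbalance in the QCT knee key secondary analyses. It rests on item (c) for month 24, and on item (b) with the Primary analyses section for months 6 and 12, as confirmed by the four QCT rows of the summary table. The tibial epiphysis is covered by the prose only.

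The gain from changing the covariate ranges from nothing at r = 0 to about 15 participants on 60 (r = 0.5, ρ = 0.5), and is smaller the more closely hip and knee baselines agree. These figures assume r and ρ, assume that hip density acts only through ρ, and for power borrow the DXA SD. The gain is minor at 30 per group and matters mostly at about 15 per group. The primary hip analysis is not affected. The change is worth making because it is nearly free: the covariate exists for every participant with a percent change, and at r = 0 it performs no differently from the hip covariate.

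**What to change.** 1. In SAP Secondary analyses (b) and (c), and in every QCT row of the Analysis Plan Summary, replace baseline total hip aBMD (or BMD) by the baseline value of the same QCT endpoint: same site, region and side.
2. State that this baseline enters as a fixed covariate. Item (b) inherits the primary model's description of its covariates as random factors, and changing the variable name alone would not secure the variance reduction.
3. Add rows for the tibial epiphysis at 6/12 months and at 24 months.
4. State the same own-baseline rule for any other CT, strength-index or finite element outcome analysed with this model.

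The cost is SAP wording and table edits. No new data, visits or participants are needed.
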